### **12.5.3 Multiplicity**

The primary and secondary endpoints will be tested at a two-sided 0.05 level of significance sequentially in the order presented in sections 7.1 and 7.2. However, to control type-1 error, the statistical testing will stop if non-significant superiority of active to vehicle ( $p>0.025$  one-sided) is observed.

### **12.5.4 Pooling of Sites**

Approximately 40 centers are planned in this study; whenever possible, approximately at least 12 subjects will be enrolled per center. In the event a center has a low number of subjects enrolled or an insufficient number of subjects with complete clearance for the stratified CMH analysis, sites will be pooled in a manner ensuring that each pooled site will have sufficient number of subjects cleared for a stratified CMH analysis.

Planning of site pooling of sites by Meta-group will be finalized prior to database lock by a statistician independent from the study team. The pooling strategy will be 1 complete clearance and 1 not complete clearance as well as 1 in each treatment group for the given age group and site. Note that each age group need not be present in each site.

### **12.5.5 Secondary Variables**

Secondary efficacy analyses will be conducted sequentially as follows for the following endpoints:

- Difference in ratio of cleared warts to all treated warts for each subject at Week 18/End of Post-treatment Efficacy Evaluation
- Difference in the proportion of subjects with complete clearance of all treated warts at Week 12, then Week 6/EOT.
- Difference in ratio of cleared warts to all treated warts for each subject at Week 12, then Week 6/EOT.
- Comparisons of reduction from baseline in wart size of treated warts at Week 18/End of Post-treatment Efficacy Evaluation

(1) For secondary efficacy variables, including

- Ratio of cleared warts to all treated warts for each subject at

---

- Week 18/End of Post-Treatment Efficacy Evaluation
- Week 12
- Week 6/End of Treatment

Ratio of cleared warts to all treated warts for each subject are defined as the ratio of the number of cleared warts out of the number of treated warts.

These endpoints will be analyzed using two-sided Wilcoxon rank sum testing at  $\alpha= 0.05$ . P value from Wilcoxon rank sum test of no difference between the 2 groups will be produced. Summary statistics will be presented for the endpoints.

(2) For secondary efficacy variables, including

- Proportion of subjects with complete clearance of all treated warts at
  - Week 12
  - Week 6/End of Treatment

Proportion of subjects with complete clearance of all treated warts is defined as the percentage of the number of subjects who have all baseline treated warts as “clinical clearance” at Week 12/week 6 out of the total subjects

These endpoints will be analyzed using the Cochran-Mantel-Haenszel (CMH) test as described in the primary efficacy analysis, including the use of age group ( $\geq 2$  to  $< 12$ ,  $\geq 12$  to  $< 18$  or  $\geq 18$ ), and site serving as the stratifying variables. The number and percentage of subjects achieving complete clearance of all treated warts (i.e., Baseline Treated warts) will be presented by group. The 95% confidence interval based on the asymptotic Wald CI will be constructed for the difference of the proportions of 2 treatments. P-value from CMH test will be presented. The Breslow-Day chi-square test for homogeneity of the odds ratios across strata will also be used to check the assumption described in the primary efficacy analysis.

(3) For secondary efficacy variables, including

- Reduction from baseline in total wart size of treated warts at
  - Week 18/End of Post-treatment Efficacy Evaluation

Reduction from baseline in total wart size (mm) at Week 18= total wart size of treated warts at Week 18 – total wart size of treated warts at baseline.

This endpoint will be analyzed using the analysis of covariance (ANCOVA) model with the group (active drug and vehicle) as fixed effect factors and the baseline total wart size, age group ( $\geq 2$  to  $< 12$ ,  $\geq 12$  to  $< 18$  or  $\geq 18$ ), and site serving as the covariates. Descriptive statistics will include the number of observations, unadjusted mean, standard deviation, median, minimum and maximum, and least squares means. Treatment differences from vehicle will be presented and

---

estimated by least squares means from the analysis model along with 95% confidence intervals and associated 2-sided p-values.

Interactions between the main effects and each of the covariates will be tested in a separate model that includes the interaction terms. If the interaction terms are significant at 0.05 level, they will be further explored using descriptive statistics for each significant interaction.

The assumptions of normality and homogeneity of variance from the ANCOVA model will be tested at 0.05 level of significance. If any failure of these assumptions is observed, a non-parametric test will be used to corroborate the results of the ANCOVA. The Shapiro-Wilk test for normality and Levene's test for the homogeneity of variance will be implemented as follows:

```
*** obtain residuals from ANCOVA;  
proc glm;  
  class site agegrp treat;  
  model change = baseline site agegrp treat / ss3;  
  output r=resid out=residual;  
run;quit;  
  
*** perform Shapiro-Wilk test;  
ods select TestsForNormality;  
proc univariate data=residual normal;  
  var resid;  
run;  
  
*** perform Levenes test;  
ods select hovtest;  
proc glm data=residual;  
  class treat;  
  model resid = treat / ss3;  
  means treat / hovtest=levene;  
run;quit;
```

If necessary, the Non-parametric ANCOVA will be performed based on Stokes et al. as follows

- 1) Separately for each site and age group, Baseline and change from Baseline will be ranked across treatments using fractional ranks with tied values being assigned the mean of the corresponding ranks;
- 2) Separate ANCOVAs will be conducted for each site and age group for the ranked change from Baseline data with the ranked Baseline result as a covariate;
- 3) The residuals from the ANCOVA models will be tested using a single CMH test for treatment effect stratified by site and age group.

If necessary, the Non-parametric ANCOVA will be implemented as follows:

\*\*\* rank baseline and change from baseline within site and age group;

---

```
proc rank nplus1 ties=mean out=ranks;
  by site agegrp;
  var change baseline;
  ranks rchg rbase;
run;

*** get residuals within each site and age group;
proc glm data=ranks;
  by site agegrp;
  model rchg = rbase;
  output r=resid out=residual;
run;quit;

*** perform stratified CMH test;
proc freq data=residual;
  table site*agegrp*treat*resid / cmh noper;
run;
```

Missing data will also be imputed for the secondary analyses on the same endpoint as the primary endpoint, but at different visits by multiple imputations.

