### 7.7.3. Randomization

Subjects that meet all inclusion and exclusion criteria will be randomized to one of two treatment groups in a 1:1 ratio for each study center according to a predetermined computer-generated randomization code.

Subjects will be randomized to treatment using an IWRS. The randomization scheme will include age stratum at 3 levels ( $\geq 2$  to  $< 12$ ,  $\geq 12$  to  $< 18$  or  $\geq 18$ ) and investigative site.

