#### **7.7.7. Efficacy Analysis**

Comparisons of proportions of subjects with all treated warts cleared will be made using Cochran-Mantel-Haenszel (CMH) test for treatment stratified by age group ( $\geq 2$  to  $< 12$ ,  $\geq 12$  to  $< 18$  or  $\geq 18$ ) and investigative site at  $\alpha = 0.05$ . Because of the low complete clearance rate, sites will be pooled in a manner ensuring that each pooled site will have sufficient number of subjects cleared for a stratified CMH analysis. The algorithm for pooling sites will be described in the SAP and finalized prior to unblinding. Comparisons of clearance rates of treated warts (number of cleared warts/number of treated warts) will be made using two-sided Wilcoxon rank sum testing at  $\alpha = 0.05$ .

For the continuous variables of wart size (diameter), analysis of covariance (ANCOVA) will be used to test CLS006 versus vehicle at Week 6/EOT, Week 18/End of Post-treatment Efficacy Evaluation and each week of the Post-treatment Efficacy Evaluation period and Follow-up period using a mixed effects model with site, age group ( $\geq 2$  to  $< 12$ ,  $\geq 12$  to  $< 18$  or  $\geq 18$ ) and Baseline Treatment Wart size (i.e., diameter) as covariates (baseline wart size will be used as a covariate for comparison of wart size).

Data listings and averages will be presented for safety measures.

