## 7.6 Predetermined Covariates and Prognostic Factors

Subject age ( $\geq 2$  -  $< 12$ ,  $\geq 12$  -  $< 18$ , and  $\geq 18$ ) and investigator site will be used as covariates for Cochran-Mantel-Haenszel (CMH) analyses.

Baseline Treatment Wart size (i.e., diameter) will also be included as a covariate in the analysis of covariance (ANCOVA).

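### The cleared-wart ratio is tested with an unstratified Wilcoxon although the trial randomises by age group and site: a valid test, but out of line with the design and with every other confirmatory analysis

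*SAP*

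**What the plan says.** **The ratio test.** SAP 12.5.5, item (1), covers the per-subject ratio at Weeks 18, 12 and 6 and states "These endpoints will be analyzed using two-sided Wilcoxon rank sum testing at" the 0.05 level. The only inferential output is described thus: "P value from Wilcoxon rank sum test of no difference between the 2 groups will be produced". Protocol 7.7.7 says that comparisons of this ratio "will be made using two-sided Wilcoxon rank sum testing". Neither text names a stratum or covariate. SAP 12.5.6 A.2 carries the same test to Weeks 2 and 4 as a tertiary analysis.

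**Randomisation.** Protocol 7.7.3 states "The randomization scheme will include age stratum at 3 levels", together with site. Protocol 7.6.3 confirms that allocation is 1:1 within age stratum at each centre.

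**The neighbouring tests.** Complete clearance at Weeks 18, 12 and 6 is tested by CMH stratified by age group and site. The wart-size ANCOVA carries both as covariates. Its rank-based fallback ranks within site and age group and ends in a stratified CMH test. SAP 7.6 says that age "and investigator site will be used as covariates for Cochran-Mantel-Haenszel (CMH) analyses"; it does not mention the Wilcoxon.

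**The sequence.** Under SAP 12.5.3 the "primary and secondary endpoints will be tested at a two-sided 0.05 level of significance sequentially", and "the statistical testing will stop if non-significant superiority of active to vehicle" is seen. The order is: primary; ratio at Week 18; complete clearance at Week 12, then Week 6; ratio at Week 12, then Week 6; wart size at Week 18. The ratio therefore fills three of the six secondary steps.

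**The concern.** Stratified randomisation balances the arms on age group and site. If those factors predict outcome, a test that ignores them counts between-stratum variation as error although the design has already removed most of it from the treatment comparison. The statistic then varies less under the null than its reference distribution assumes, so the test can be conservative and lose power.

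The ratio is the only confirmatory endpoint tested without the randomisation factors, and no reason is given. At stake are some power at three steps of a fixed sequence, and a set of p-values that do not all rest on the same adjustment.

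**Working it through.** **1. The plan's own figure.** The only stated power is for the primary endpoint (10% v 2%, two-sided 0.05). With pooled variance under the null,

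power = Φ{[Δ − 1.96·√(2p̄(1−p̄)/n)] / √[(p₁q₁ + p₂q₂)/n]}, where Δ = 0.08 and p̄ = 0.06.

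- n = 200 per arm: (0.08 − 1.96 × 0.02375)/0.02341 = 1.43, giving 92.4% (stated 92%).
- n = 240 per arm: (0.08 − 1.96 × 0.02168)/0.02137 = 1.76, giving 96.0% (stated 96%).

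Both reproduce. Neither document gives an effect size or power for the ratio, so the rest depends on assumptions.

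**2. The two tests.** Let R_h be the active-arm rank sum in stratum h, with n_h subjects, m_h of them active, and E_h = m_h(n_h+1)/2. The van Elteren statistic is

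Z = Σ w_h(R_h − E_h) / √(Σ w_h²V_h), with w_h = 1/(n_h+1) and V_h the tie-corrected permutation variance.

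The planned Wilcoxon is the case of a single stratum.

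**3. Inputs.** From the documents: 480 subjects, about 40 sites, 1:1 allocation, 1 to 6 warts, and ages 80/80/320, which is 2/2/8 per site of 12. Unpooled, there are 40 × 3 = 120 cells of 480/120 = 4 subjects on average. Assumed, because not in the documents: site SD and age effect (youngest v adult) on the logit scale, block size, wart-count distribution, and a treatment log odds ratio of 0.7 to 0.8, chosen to leave power mid-range (complete clearance about 1% v 2%, well below the planned 2% v 10%).

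**4. Results.** There were 3000 simulated trials per setting; the Monte Carlo SE is about 0.004 for size and 0.009 for power. Entries are planned test / van Elteren by age × 8 pooled sites / van Elteren by age × unpooled site.

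| Strata effects (site SD = age effect) | Two-sided size | Power | Gain, pooled − planned |
|---|---|---|---|
| None | 0.044 / 0.044 / 0.043 | 0.569 / 0.571 / 0.557 | +0.2 points |
| Mild, 0.5 | 0.048 / 0.049 / 0.049 | 0.557 / 0.560 / 0.554 | +0.3 |
| Moderate, 1.0, blocks of 2 | 0.043 / 0.046 / 0.053 | 0.515 / 0.535 / 0.534 | +2.0 |
| Moderate, 1.0, blocks of 4 | 0.042 / 0.046 / 0.046 | 0.520 / 0.526 / 0.490 | +0.6 |
| Strong, 1.5 | 0.034 / 0.043 / 0.055 | 0.471 / 0.518 / 0.528 | +4.7 |
| Strong, 1.5, no extra subject variation | 0.031 / 0.038 / 0.054 | 0.520 / 0.583 / 0.613 | +6.3 |

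Rows without a stated block size used blocks of 2.

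**5. Why size falls.** If Z has null standard deviation s, its true size is 2[1 − Φ(1.96/s)]. The planned test had s = 0.976 with no strata effects, giving 0.045. It had s = 0.934 and 0.905 in the two strong settings, giving 0.036 and 0.030. These match the simulated 0.044, 0.034 and 0.031.

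**6. A second simulation** (10 pools, 1500 trials per setting) gave, planned v pooled-site stratified, 62.7% v 61.8% with no strata effects and 61.3% v 61.9% at site SD 1.0 with blocks of 2. At this level the sign of the difference is not settled.

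**7. The sequence.** The Week 12 and Week 6 ratio tests are reached only after complete clearance has passed at Weeks 18, 12 and 6. A simulation of the whole chain (400 trials in each of six scenarios, site SD 0.5 to 1.5, effects assumed) put the probability of passing through the Week 6 ratio at 11.5–15.3% with the planned test and 11.5–15.0% with the stratified one, never more than 0.25 points apart. The limiting step was complete clearance at Week 6, with power 16–21%. Given success on the primary, the Week 18 ratio passed in at least 97.8% of trials with either test.

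**The case against.** The case for leaving the test alone is strong. It is pre-specified identically in protocol and SAP, it is valid, and its size stayed below 0.05 in every setting tried. SAP 7.6 assigns age and site to the CMH analyses and promises nothing for the Wilcoxon, so there is no contradiction to resolve. The gain is visible only at a site SD that the documents do not support or exclude. Reusing the site pools also has a cost: SAP 12.5.4 forms them from counts of complete clearance, an outcome closely related to the ratio, and does not say whether the same pools serve Weeks 12 and 6.

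All of this stands as a limit on size. It does not explain why one confirmatory endpoint departs from the randomisation and from every neighbouring test, including the rank-based fallback for wart size. The pooling difficulty is met by a sentence in the SAP.

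A reader might infer from the place of the ratio in the sequence that power lost here costs the later claims. The documents do not support that: the order of testing puts the complete-clearance tests ahead of the Week 12 and Week 6 ratios, and at the planned effect the Week 18 ratio has power near 100% with or without strata.

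**Conclusion.** The point holds as one of alignment, with a conditional and mostly small efficiency element. The planned Wilcoxon ignores both randomisation factors. It becomes clearly conservative (size 0.031–0.034) and gives up about 5 to 6 points of power only under the strongest age and site effects assumed. With none to moderate effects the stratified test by pooled site differs by about zero, or by a point or two in either direction. How prognostic age and site are, the block size and the effect on the ratio are all assumed.

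Two stronger readings should be resisted. One is that ignoring the strata invalidates the p-values or inflates type I error; any departure is in the conservative direction. The other is that the test is conservative as it stands; that requires strong strata effects, which the documents do not quantify. The primary analysis is not affected.

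**What to change.** 1. In SAP 12.5.5(1), SAP 12.5.6 A.2 and Protocol 7.7.7, replace the Wilcoxon with a stratified Wilcoxon (van Elteren) test by age group and pooled site. In SAS this is PROC FREQ with CMH2 and SCORES=MODRIDIT.
2. Do not stratify by the roughly 120 unpooled site-by-age cells. With about 4 subjects per cell, power fell below that of the planned test in one moderate setting (0.490 v 0.520).
3. State in SAP 12.5.4 that one set of pools, fixed blind before database lock, applies to the ratio at all visits, and acknowledge that the pooling rule is built on complete-clearance counts.
4. Record the change in SAP 4.1, which at present lists none.

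The cost is a small programming change and a few sentences. The multiple-imputation combination code is untouched, since SAP 12.5.5 extends imputation only to complete clearance at the other visits. The downside is small: if age and site are not prognostic, power for the ratio may fall by a point or two.

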## 6.0 Study Design

The study will be conducted as a randomized, double-blind, vehicle-controlled, parallel group, multicenter study at approximately 40 sites involving approximately 480 subjects (~240 per treatment group) with nongenital cutaneous common warts. Approximately 160 subjects enrolled will be pediatric subjects (~80 will be  $\geq 2$  to  $<12$  years of age and ~80 will be  $\geq 12$  to  $<18$  years of age). Subjects may be in the study up to 34 weeks.

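### The non-parametric wart-size check ranks and fits within each site and age group cell; unless the pooled sites apply, many paediatric subjects carry no information and the check loses power (minor)

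*SAP*

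**What the plan says.** SAP 12.5.5 analyses the Week 18 reduction in total wart size by ANCOVA. If the Shapiro-Wilk or Levene test rejects at 0.05, "a non-parametric test will be used to corroborate the results of the ANCOVA". That test has three steps:

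- Baseline and change are ranked within each site and age group.
- "Separate ANCOVAs will be conducted for each site and age group for the ranked change from Baseline data", with ranked baseline as covariate. The code comment is "get residuals within each site and age group" and the model is "model rchg = rbase", run by site and age group.
- "The residuals from the ANCOVA models will be tested using a single CMH test for treatment effect stratified by site and age group".

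SAP 6.0 describes a "multicenter study at approximately 40 sites involving approximately 480 subjects", with about 80 subjects aged 2 to under 12 and about 80 aged 12 to under 18. SAP 12.5.4 aims for a centre size such that "approximately at least 12 subjects will be enrolled per center". It also plans to pool sites that are small, or that have too few clearances, for the stratified CMH analysis. SAP 12.5.5 does not say that those pools define site in the non-parametric ANCOVA.

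**The concern.** A regression with an intercept and a slope needs more than two subjects before it leaves any residual. If site means the original centre, the typical paediatric cell has about two subjects. Those children are fitted exactly and add nothing to the treatment comparison. Adult cells, with about eight subjects, each use up a separate slope and are ranked against only seven others.

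The check is meant to support the wart-size result when the ANCOVA assumptions look doubtful. A check that is silent on many of the children, and weak overall, could fail to corroborate a real effect. The same ANCOVA method is carried to Weeks 2, 4, 6 and 12 in SAP 12.5.6, though those comparisons are descriptive.

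**Working it through.** **The plan's own power figure.** SAP 6.1 gives power only for the primary endpoint (10% v 2%). With pooled variance, power = Φ[(0.08 − 1.96·√(2·0.06·0.94/n)) / √((0.10·0.90 + 0.02·0.98)/n)].
- n = 200 per arm: (0.08 − 0.0465)/0.0234 = 1.43, giving 92.4% (stated 92%).
- n = 240 per arm: (0.08 − 0.0425)/0.0214 = 1.76, giving 96.0% (stated 96%).

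No power, effect or SD is stated for wart size, so everything on power below rests on assumptions.

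**Cell sizes.** Adults number 480 − 160 = 320. Per site this gives 80/40 = 2, 80/40 = 2 and 320/40 = 8.

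**Subjects in cells of two or fewer.**
- Exactly 2/2/8 at every site: 160 of 480.
- 12 per site with a random age mix: a child's cell has at most two members if at most one of the other 11 subjects is in the same age group (probability 80/480 = 1/6 each). (5/6)^11 + 11·(1/6)·(5/6)^10 = 0.135 + 0.296 = 0.431, and 0.431 × 160 = 69. Simulation also gave about 69.
- Unequal sites (simulated): about 59.

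A cell of n leaves n − 2 residual degrees of freedom, so residuals are zero for n ≤ 2. The exception is a pair with tied baselines, where no slope is fitted; with integer-millimetre sizes this affected about 1 to 5 subjects per trial. Counting single-arm cells as well, about 85 to 91 of 480 subjects (18% to 19%) contributed nothing under a random age mix.

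**Power.** The SAP procedure was simulated with 480 subjects, 40 sites and blocked 1:1 allocation (2,000 runs per setting, Monte Carlo error about 1 point). The comparator is one rank ANCOVA with a common baseline slope and site and age group as factors. Assumed effects gave the parametric ANCOVA about 80% or 90% power (normal data) and about 55% to 74% (integer-mm data with ties). No site effect was simulated. The pooled setting uses 29 strata, from 240·0.10 + 240·0.02 = 28.8 expected clearances, taken as 19 adult + 5 + 5.

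| Strata | Data | SAP method v one rank ANCOVA, smaller effect (%) | Same, larger effect (%) | Loss (points) |
|---|---|---|---|---|
| Unpooled, exactly 2/2/8 | normal | 47.7 v 78.0 | 59.6 v 89.2 | 30.3, 29.6 |
| Unpooled, 12 per site, random age mix | normal | 54.4 v 77.4 | 67.3 v 89.1 | 23.0, 21.8 |
| Unpooled, unequal sites | normal | 54.7 v 74.5 | 71.4 v 88.1 | 19.8, 16.7 |
| Paediatric cells pooled only | normal | 65.0 v 74.6 | 80.5 v 88.5 | 9.6, 8.0 |
| 29 pooled strata | normal | 72.0 v 78.2 | 85.4 v 89.2 | 6.2, 3.8 |
| Unpooled, exactly 2/2/8 | integer mm | 36.5 v 62.0 | 48.2 v 76.6 | 25.5, 28.4 |
| Unpooled, 12 per site, random age mix | integer mm | 40.9 v 61.0 | 55.4 v 76.8 | 20.1, 21.4 |
| Unpooled, unequal sites | integer mm | 43.8 v 59.8 | 60.2 v 76.7 | 16.0, 16.5 |
| Paediatric cells pooled only | integer mm | 54.0 v 62.6 | 69.0 v 76.1 | 8.6, 7.1 |
| 29 pooled strata | integer mm | 56.2 v 59.8 | 71.8 v 75.0 | 3.6, 3.2 |

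**Sources of the loss.** Take 12 per site, random age mix, normal data and the smaller effect. A common slope within the same cells raises power from 54.4% to 65.0% (10.6 points). The remaining 77.4 − 65.0 = 12.4 points come from ranking in fine strata. Ignoring baseline altogether in the same cells gave 58.4%, more than the separate slopes achieve.

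**Near the ceiling.** In separate runs with skewed shrinkage (700 trials per effect), the SAP method against ranking by age group alone gave 52% v 78%, 76% v 95% and 89% v 99%, losses of 26, 19 and 10 points.

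**Site effects.** These runs used 250 trials per setting (error about 3 points), again against age group alone.
- No site effect: 51 v 78, 74 v 93, 88 v 99.
- Latent site correlation about 0.2: 52 v 67, 77 v 88, 90 v 98.
- About 0.4, smallest effect only: 52 v 52.

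Stratifying by age group and four-site pools beat the unpooled method by about 5 to 16 points at site correlations from 0 to 0.4, without inflating type I error.

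**Type I error.** The unpooled SAP method on normal data gave 4.5% to 5.8%.

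**The case against.** The strongest objection is that pooling may already apply. SAP 12.5.4 pools sites for a stratified CMH analysis, and this procedure ends in one. The primary CMH code in SAP 12.5.2 also writes plain site where pooling is clearly intended, and that section notes that variable names may differ. Protocol 7.7.10 extends pooled-centre summaries to secondary endpoints. This has weight: under pooling the cells of two or fewer vanished in simulation. But SAP 12.5.2 also defines site as the investigative site for the imputation model, and 12.5.5 is silent, so a programmer could follow either reading.

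Ranking within site and age group also matches the randomisation strata and follows the method the SAP cites. That stands as a reason to keep site in the analysis. It does not justify a separate slope in cells of two.

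A reader might infer more than the documents support:

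- **A fixed loss of about 20 to 25 points.** No wart-size effect, SD or site variation is given, and the result depends on layout, comparator and nearness to the power ceiling.
- **That the check is certain to be run.** Shapiro-Wilk rejected in 100 of 100 trials checked at each setting, but skewed shrinkage had been assumed. Rejection is likely, not certain.
- **That site should simply be left out.** The gain from doing so can disappear when site effects are strong.

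**Conclusion.** The point holds as a minor one. If site means the original centre, as the code reads, cells of two or fewer give zero residuals (tied baselines excepted). Roughly 18% of subjects contribute nothing under a random age mix, and a third (160 of 480) if every site were exactly 2/2/8.

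The power cost is roughly 10 to 30 points with unpooled sites, smaller near the ceiling. It is about 3 to 10 points if the SAP 12.5.4 pools apply. Measured against ranking by age group alone, it can shrink towards none when site effects are strong. These ranges rest on assumed effects, distributions, site sizes and an approximate number of pooled strata.

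The consequence is limited. Type I error, the primary endpoint and the parametric wart-size ANCOVA are untouched. The affected test only corroborates, no rule lets it overturn the ANCOVA, and wart size is the last endpoint in the fixed sequence of SAP 12.5.3.

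**What to change.** Before unblinding, choose one of these in SAP 12.5.5:

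- **Pooled strata.** State that the non-parametric ANCOVA ranks, fits and stratifies by age group and the pre-set pooled site. Replace site with the pooled-site variable in the BY statements of PROC RANK and PROC GLM and in the TABLE statement of PROC FREQ.
- **One rank ANCOVA.** Use overall ranks with a common baseline slope, and site and age group as factors. This keeps site adjustment.

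Do not drop site entirely. The cost is a few lines of SAS and one SAP sentence. The downside of the pooled option is that site is adjusted only at pool level in this check.
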